1. STUDY OBJECTIVES

1.1 Primary Objective

The co-primary clinical outcomes are changes in pain and disability. We will examine immediate clinical outcomes as a function of treatment. Relative to the control group, participants in the experimental group will show greater reductions in pain and

disability at post-treatment relative to pre-treatment baseline (Hypothesis 1). To test Hypothesis 1, we will examine the Treatment by Time (baseline-post treatment) interaction in a LME model: a greater reduction in pain and disability in the experimental group than in the control group. The co-primary clinical outcomes of changes in pain and disability will be assessed at 1-, 6-, 12-, 24-, and 48-weeks post-treatment.

1.2 Secondary Objectives

Secondary objectives are to examine potential mechanisms of pre- to post-treatment changes in clinical outcomes and maintenance of treatment gains. Participants in the experimental group will exhibit greater pre- to post-treatment decreases in pain/harm expectancy and increases in lumbar flexion as compared to the control group (Hypothesis 2.1). Decreases in pain/harm expectancy and increases in lumbar flexion will be positively related to pre- to post-treatment reductions in pain and disability (Hypothesis 2.2). Examination of maintenance of treatment gains will occur at 1-, 6-, 12-, 24-, and 48-weeks post-treatment. Relative to the control group, participants in the experimental group will continue to show lower levels of pain and disability at each time point as well as increased activity in their natural environment (Hypothesis 3).

2. BACKGROUND AND RATIONALE

2.1 Background on Condition, Disease, or Other Primary Study Focus

Low back pain is the second most common reason for a visit to a physician, with direct medical costs exceeding \$90 billion per year in the United States alone.^{9, 10} These costs are driven primarily by 7-10% of patients who develop chronic low back pain (CLBP) that can last for many years.⁹⁻¹¹ Fear of movement (i.e., kinesiophobia) due to expectations of pain and harm is an important risk indicator for the development of persistent pain and disability, with studies consistently showing that high fear is one of the strongest predictors of the transition from sub-acute to CLBP.¹²⁻¹⁵ Specifically, fear encourages the adoption of maladaptive movement patterns wherein tasks of daily living are performed with reduced lumbar spine flexion and compensatory increases of knee, hip, and shoulder flexion. Using our standardized reaching tasks, we have repeatedly demonstrated reduced lumbar spine flexion in fearful acute, sub-acute, and CLBP sufferers.¹⁶⁻²⁰ While avoidance of lumbar flexion may benefit these CLBP sufferers in the short-term by reducing their fear of injury, in the long-term, limited lumbar flexion becomes an entrenched pattern that can lead to shortening of spinal peri-articular connective tissues, changes in surrounding muscles,²¹⁻²³ and increased risk for chronicity.

The current standard of care for individuals with high fear and CLBP is graded exposure therapy, which promotes gradual confrontation of avoided movements in order to reduce expectations of pain/harm.²⁴ Although recent RCTs with CLBP patients indicate that this approach significantly reduces fear of movement, it has not led to greater reductions in disability when compared to standard therapy.^{4, 6} We posit that prior studies have not seen the full benefit of this approach because they have failed to make restoration of lumbar flexion an explicit focus of therapy. Without this goal, patients are able to complete the graded movement tasks using maladaptive movement patterns that can impede full recovery. Therefore, we hypothesize that explicit efforts to increase lumbar flexion are required to benefit those with CLBP who are typically viewed as having intractable pain and disability.²⁵

With the support of an NIH R21, we completed a Phase I trial of an immersive virtual reality dodgeball game designed specifically to increase lumbar flexion among individuals with CLBP and high fear of movement. The results of this proof-of-concept study demonstrated that 3 daily sessions of virtual dodgeball was safe, did not exacerbate existing back pain, was highly rated by participants, and increased lumbar spine flexion during gameplay. The current Phase II RCT will determine the efficacy of a 9-week course of treatment of virtual dodgeball to reduce pain and disability among individuals with CLBP and high fear of movement.

2.2 Study Rationale

2.2.1 Epidemiology of Low Back Pain

Low back pain (LBP) is one of the most common reasons for seeking medical care and accounts for over 3.7 million physician visits per year in the United States alone.⁹ It is the leading cause of pain in the U.S., affecting 28.1% of adults each year¹¹ and 90% of adults in their lifetime.^{9, 26-31} Back pain is associated with \$200 billion in lost wages and productivity annually, and is the second leading contributor to annual disability costs of \$300 billion.⁹⁻¹¹ These costs are driven largely by 7-10% of patients who develop chronic low back pain (CLBP) that typically lasts for many years.²⁶ According to Foster (2011), “Despite decades of research and improved quality of clinical trials, the reality is that the treatments we have to offer patients tend to produce small effects, often only in the short term and none appear to change effectively the longer-term prognostic paths or trajectories for patients.”²⁷

2.2.2 Fear-Avoidance Model of Low Back Pain

The fear-avoidance model of low back pain explains why some people with acute musculoskeletal pain go on to develop chronic pain and disability.^{32, 33} Central to this model, individuals who have high kinesiophobia are prone to catastrophic thoughts (e.g., “The pain will get worse!”), are more likely to experience greater fear of movement and re-injury, and hence will engage in behavioral adaptations to avoid or escape pain. In contrast, individuals with low kinesiophobia have little fear of movement and re-injury, and therefore are more likely to confront potential or actual pain-provoking situations that are needed to progress towards recovery (e.g., return to daily activities, work, rehabilitation). While the fear-avoidance model posits a generic avoidance of all forms of movement that are perceived as threatening, we have repeatedly shown that individuals with high fear and LBP display very similar patterns of motor behavior – they specifically avoid flexion of the lumbar spine.^{16, 34, 35} Over time, avoidance of lumbar spine motion increases the risk for re-injury due to shortening of peri-articular connective tissues and changes in the surrounding muscles.²¹⁻²³ These changes increase the risk of injury when the individual is exposed to common, unexpected environmental challenges (e.g., slipping on ice). Thus, interventions for individuals with CLBP and high fear must explicitly address avoidance of lumbar flexion.

2.2.3 Virtual Reality Games for Health Promotion and Rehabilitation

Virtual reality (VR) games have been used to promote health education, disease management, distraction from discomfort, increased physical activity, and rehabilitation involving motor performance, such as following a stroke.³⁶⁻³⁸ Further, strong evidence has accumulated regarding the utility of VR gaming for short-term pain relief.^{39, 40} One of the clear positive benefits of games is that they motivate

players to compete and score points. Games also provide a level of distraction from the actual behavior being performed, and individuals are willing to engage in behaviors that might cause pain due to the competitive nature of the game.⁴¹ Consistent with this notion, VR gaming has been shown to significantly reduce pain during burn debridement, wound dressings, painful activity, and uncomfortable medical procedures.^{39, 40} However, to date, VR gaming interventions have not been adapted to address CLBP,^{39, 40} and have not taken advantage of VR interface features (e.g., full-body control of avatars, real time feedback/reinforcement).

2.2.4 Mechanisms Underlying Proposed Game Intervention

Both Graded Activity (GA) and Graded Exposure (GE) are common approaches to the treatment of CLBP. Graded activity focuses on restoring function regardless of pain. The intervention begins with provision of a treatment rationale emphasizing the negative effects of inactivity and the positive effects of physical activity on well-being, and then uses a combination of activity quotas and positive reinforcement to promote increased activity over time. In contrast, GE focuses on reducing fear of pain and expectations of harm upon movement. Treatment begins with provision of a treatment rationale emphasizing the role of fear as an impediment to functional restoration, and then proceeds with development of an individualized hierarchy of feared movements to guide subsequent sessions of graded exposure. Systematic exposure to feared movement provides repeated opportunities to confront and correct patient misperceptions of the expected relationship between movement and risk of harm. RCTs have shown that both GA and GE produce significant reductions in pain and disability, and that these intervention effects do not differ significantly at post-treatment and 1-, 6-, and 15-month follow-up intervals.^{4, 6, 42} However, a systematic literature review concluded that GA is no more effective than other forms of exercise and that GE is no better than wait-list or usual care controls.⁴³ We hypothesize that GA and GE approaches to CLBP fail to outperform other forms of exercise or usual-care controls because patients can complete the prescribed tasks with restricted lumbar spine motion simply by increasing motion at the ankles, knees, and hips. Indeed, continued restriction of lumbar spine motion may be a key impediment to optimal restoration of function as we have consistently demonstrated that pain-related fear is associated with restricted lumbar flexion among: 1) individuals with subacute LBP,^{16, 35} 2) individuals with CLBP,¹⁸ 3) asymptomatic individuals who have recently recovered from LBP,³⁴ and 4) healthy individuals with experimentally-induced back pain.¹⁹ To address the ubiquitous and persistent problem of restriction of lumbar spine flexion among those with pain-related fear, we specifically designed a suite of virtual reality games (i.e. VR Dodgeball) that necessitate progressively larger excursions of the lumbar spine to successfully complete the games. Similar to GA, we believe that our intervention does not require an explicit focus on psychological factors related to avoidance behavior, but rather operates through a combination of acute distraction from pain, repeated reinforcement of movement goals with feedback of progress, and graded increases in expectations of spinal lumbar flexion across sessions. In a Phase I trial, we demonstrated that individuals with CLBP and pain-related fear who played virtual dodgeball had significant increases spinal motion across sessions. They also rated the game as highly enjoyable and had no adverse outcomes. With sufficient exposure to this intervention, we posit that individuals with CLBP and pain-related fear will develop an implicit understanding that lumbar spine motion is not dangerous and will generalize the unrestricted lumbar spine motion that is promoted by the

game to their daily lives. In so doing, we expect that they will restore the normal patterns of spinal motion that are necessary to promote a lasting recovery.

3. STUDY DESIGN

The proposed project is a Phase II RCT in which CLBP participants will be randomly assigned to one of two intervention arms. Those assigned to the experimental group will play our immersive video games that encourage participants to produce progressively larger lumbar flexion excursions at each game level and across treatment sessions. Those in the control group will play the same immersive games but the parameters will be modified such that only small excursions of lumbar flexion are needed to successfully complete gameplay. Treatment frequency and duration is based on existing evidence that graded activity and graded exposure interventions, typically lasting 6-12 weeks with 8-18 treatments sessions, result in significant reductions in disability.^{44, 43} Accordingly, participants in the proposed study will complete 18 intervention visits over 9 weeks with the number of sessions tapered across weeks (i.e., 3 sessions/week in weeks 1-3, 2 sessions/week in weeks 4-6, and 1 session/week in weeks 7-9). Our co-primary outcome variables will be change in pain and change in disability from baseline to 1-week post-treatment (Aim 1). We will also examine changes in expectations of pain/harm and lumbar flexion as potential mechanisms of change in pain and disability (Aim 2). Aim 3 will examine maintenance of treatment gains at 1-, 6-, 12-, 24-, and 48-weeks post-treatment.

4. SELECTION AND ENROLLMENT OF PARTICIPANTS

According to the most recent statistics from the U.S. National Health Interview Survey (NHIS), when collapsing across gender, approximately 29.2% of Whites, 27.2.0% of Blacks/African Americans, and 27.4% of Hispanics reported low back pain in the previous three months. These data, shown in the table below are adapted from the Summary Health Statistics for U.S. Adults: National Health Interview Survey published in 2012. Although these national statistics indicate that low back pain is slightly more common amongst Whites as compared to African Americans and Hispanics, we will recruit our sample to ensure that it meets or exceeds the proportion of ethnic and racial minorities in the population according to 2010 U.S. Census figures. Specifically, we plan to enroll 16% Hispanic and 84% Non-Hispanic participants as well as 73% White, 17% African American, 7% Asian American, 2% American Indian/Alaskan Native, and 1% Native Hawaiian or Other Pacific Islander.

Planned Inclusion Enrollment

Racial Categories	Ethnic Categories				Total	
	Not Hispanic or Latino		Hispanic or Latino			
	Female	Male	Female	Male		
American Indian or Alaska Native	1	1	0	0	2	
Asian	8	8	0	0	16	
Native	1	1	0	0	2	

Hawaiian or Other Pacific Islander					
Black or African American	16	16	4	3	39
White	71	70	15	15	171
More than One Race	0	0	0	0	0
Unknown or Not Reported	0	0	0	0	0
Total	97	96	19	18	230

Using recruitment procedures that we have successfully employed in prior CLBP trials (R01 AT00697, R21AR064430, R21AR063909) as well as prior cohort studies,^{18, 35, 45-48} we will recruit 230 participants with CLBP and fear of movement. We will include participants with CLBP between the ages of 18-60 and who report no health condition(s) that may restrict movement or preclude safe participation. Participants will be recruited through advertisements and flyers posted in the local community, and via a combination of electronic, radio, print, and possibly television announcements in the local and surrounding communities. We may also recruit from local clinics. Finally, ResearchMatch.org will be used as a recruitment tool for this protocol. ResearchMatch.org is a national electronic, web-based recruitment tool that was created through the Clinical & Translational Science Awards Consortium in 2009 and is maintained at Vanderbilt University as an IRB-approved data repository (see IRB #090207).

4.1 Inclusion Criteria

Participants must meet all of the following inclusion criteria:

- 18-60 years of age
- Low back pain that has been ongoing for at least half the days in the last 6 months
- Average pain intensity of 3 or higher over the past week on a 0-10 Numerical Rating Scale
- Disability >4 on Roland and Morris Disability Questionnaire
- Tampa Scale for Kinesiophobia score >36
- Has sought care or consultation from a health care provider for back pain
- Meets category < 4 on the Classification System of the Quebec Task Force on Spinal Disorders,⁴⁹ which reflects low back pain without neurological signs
- Working proficiency in English

4.2 Exclusion Criteria

Candidates meeting any of the following exclusion criteria at baseline will be excluded from study participation:

- Has a personal history of the following neurological disorders: Alzheimer's, Amyotrophic Lateral Sclerosis, Multiple Sclerosis, Parkinson's, Neuropathy, Stroke, Seizures
- Has a personal history of the following cardiorespiratory disorders: Congestive heart failure, heart attack in past 2 years
- Has a personal history of the following musculoskeletal disorders: Rheumatoid Arthritis, muscular dystrophy, pathologic fractures of the spine, avascular necrosis or osteonecrosis, severe osteoarthritis
- History of spine surgery or a hip arthroplasty
- Has active cancer
- Has a chronic disease that may restrict movement or preclude safe participation
- Has used opioids within 30 days prior to study enrollment
- Reports being pregnant, lactating, or that they anticipate becoming pregnant within 2-months
- Reports pending litigation related to CLBP
- Has current drug or alcohol use or dependence that, in the opinion of the PIs, would interfere with adherence to study requirements
- Has significant visual impairment that would prevent virtual reality headset use
- Has significant motion sickness that would prevent virtual reality headset use

4.3 Study Enrollment Procedures

When an individual expresses interest in the study, he or she will be directed to complete an online or phone Prescreen Assessment Questionnaire (CRFs VIGOR Pre-Screen) after providing assent to the prescreen. If a potential participant passes the initial eligibility screening, the study coordinator will contact the potential participants by e-mail and/or by phone to schedule a full screening assessment (Visit 0). At this time the study coordinator will verbally describe the study to the potential participant and answer any questions. The consent process will be conducted in a quiet, private room. During the consent process, potential participants will be informed about the study purpose and procedures and be given the opportunity to ask questions. They will be shown a video of the game to help them with the process. If they wish to continue, they will be asked to read and sign an informed consent document. Next, a member of the research team will review the signed consent form and will ask the participant to explain the procedures in their own words to ensure that they comprehend the study procedures before proceeding to the initial assessment.

Participants will then complete the screening visit surveys. Based on the responses to the questions, interested individuals who meet the inclusion/exclusion criteria will be identified and then undergo a physical exam by a licensed physical therapist or

physician. Participants who remain eligible following the physical exam will then be formally enrolled into the study. The study coordinator will then randomly assign them to their respective intervention group using a sex-stratified random allocation table.

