6. STUDY PROCEDURES

6.1 Schedule of Evaluations

Assessment	Prescreen	Screen Visit 0	Enrollment & Baseline Visit 1	Treatment Visits 2-19	Post-Treatment Assessments Visit 20	Post-Treatment Assessments Visits 21-24
Numeric Pain Rating Scales 7-day & 24-hour	X	X	X	X*	X	X
Roland-Morris Disability Questionnaire	X	X	X		X	X
Fear Question	X	X				
Medical History - Back Pain	X	X				
Medication Log		X	X	X	X	X
Informed Consent Form		X				
Inclusion/Exclusion Criteria		X				
Enrollment/Randomization		X				
Medical History		X				
Physical Exam Form		X				
Adverse Events			X	X	X	X
Numeric Pain Rating Scale - Right Now			X	X	X	X
Standardized Reaching Paradigm • Pain & Harm Expectancy • Lumbar Spine Flexion			X	X*	X	X
Tampa Scale for Kinesiophobia			X		X	X
Center for Epidemiologic Studies - Depression			X		X	X
Pain Catastrophizing Scale			X		X	X
Pain Resilience Scale			X		X	X
Pain Self Efficacy Questionnaire			X		X	X
Brief Pain Inventory - Short Form			X		X	X
PROMIS-Anxiety			X		X	X
PROMIS-Depression			X		X	X
PROMIS-Positive Affect			X		X	X
PROMIS – Meaning and Purpose Scale			X		X	X
Life Fulfillment Scale			X		X	X
Profile of Mood States			X		X	X
Real World Activity Monitoring			X		X	X
Treatment Evaluation Inventory - Short Form			X		X	
Patient Global Impression of Change					X	X

*assessed at the first visit of each week

Note: Prescreening, Visit 0 screening, Visit 1 baseline, and Visit 2 first intervention can all occur on the same day.

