6.2.1 Screening Evaluation

Consenting Procedure

The consent process will be conducted in a quiet, private room. During the consent process, potential participants will be informed about the study purpose and procedures and be given the opportunity to ask questions. They will be shown a video of the game to help them with the process. If they wish to continue, they will be asked to read and sign a single informed consent document. Next, a member of the research team will review the signed consent form and will ask the participant to explain the procedures in their own words to ensure that they comprehend the study procedures before proceeding to the initial assessment. Informed consent must be obtained before participants are screened. A copy of the signed and dated consent form will be given to participants, and the original document will be electronically stored on a secure server.

Pre-Screening

The purpose of pre-screening is to determine if the research candidates will qualify for the research. This web-based survey will take approximately 15-minutes to complete and includes the following forms:

- Numeric Pain Rating Scales 7-day & 24-hour
- Roland-Morris Disability Questionnaire
- Fear Question
- Medical History – Back Pain

Screening (Visit 0)

The purpose of the screening visit is to 1) describe the study protocol to candidates and begin the informed consent process, and 2) determine if study candidates will qualify for the study. The screening visit will take approximately two hours. During the screening visit the study coordinator will complete, in cooperation with the study candidate, the following:

- Numeric Pain Rating Scales 7-day & 24-hour
- Roland-Morris Disability Questionnaire
- Fear Question
- Medical History – Back Pain
- Medication Log
- Quebec Task Force Classification
- Informed Consent Form
- Inclusion/Exclusion Criteria Form
- Enrollment & Randomization Form
- Medical History
- Physical Exam

Re-screening participants may be considered and reviewed by the PIs on a case-by-case basis. Screening must occur within 30-days of prescreen completion. Visits 1 and 2 (Baseline and Intervention 1) may occur on the same day as screening and must occur within 7 days of screening. If these deadlines are not met the participants will be assigned a new PID, re-screened, and re-consented.

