6.2.2 Enrollment, Baseline, and/or Randomization (Visit 1)

Enrollment

A single informed consent form that describes both screening and study procedures will be used. The date of enrollment in The VIGOR Study will be defined as the date all of the screening criteria are met and the individual agrees to participate. The enrollment date will be recorded on a case report form along with the allowable window between screening and randomization.

- CRF: Randomization and Enrollment Form

Baseline Assessments

Participants enrolled in the study will complete the following baseline assessments at Visit 1:

- Numeric Pain Rating Scales 7-day & 24-hour
- Roland-Morris Disability Questionnaire
- Medication Log
- Adverse Events Log
- Numeric Pain Rating Scale – Right Now
- Standardized Reaching Paradigm (Pain & Harm Expectancy, Lumbar Spine Flexion)
- Tampa Scale for Kinesiophobia
- Center for Epidemiologic Studies – Depression
- Pain Catastrophizing Scale
- Pain Resilience Scale
- Pain Self Efficacy Questionnaire
- Brief Pain Inventory – Short Form
- PROMIS-Anxiety
- PROMIS-Depression
- PROMIS-Positive Affect
- PROMIS-Meaning and Purpose Scale
- Life Fulfillment Scale
- Profile of Mood States
- Real World Activity Monitoring
- Treatment Evaluation Inventory – Short Form

Randomization

The study coordinator will use a sex-stratified random allocation table, created by the study statistician, to assign participants to a treatment group. A maximum of 7-days will be permitted between enrollment and randomization or initiation of the study intervention.

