9.2 Sample Size and Randomization

We will recruit 230 participants with chronic low back pain (CLBP) and fear of movement. We will include participants with CLBP between the ages of 18-60 and who report no health condition(s) that may restrict movement or preclude safe participation. Participants will be recruited from the general population and specific

organizations such as Virginia Commonwealth University's University Medical Associates.

Aim 1: Power analyses were conducted to determine the sample size needed to achieve clinically important differences in our co-primary clinical outcome measures of pain and disability. Based on the extant literature, we based our analyses on a \geq 30% decrease in pain ratings¹ (on the 0-10 NRS scale) and a 30% decrease in disability ratings on the RMDQ² in the experimental group. Further, we predict a 10% decrease in pain and disability in the control group to account for potential placebo effects. The population standard deviations were set at 75% of the population mean values. The pre-post correlation was estimated as $r=0.7$. These population parameters translate into an effect size of $f=0.30$. Using these parameters, we drew 10,000 samples from a normal population distribution. Based on these parameters, to achieve power of 80% and $\alpha=0.05$ will require a total $N=78$.

Aim 2 & 3: Power analyses were conducted to determine the sample size needed to address hypotheses 2.1, 2.2, and 3. Using the method described by Morris (2008),³ we calculated effect size estimates from randomized clinical trials on the effects of graded activity or graded exposure interventions on changes in disability among individuals with CLBP.⁴⁻⁷ For our power analyses, we adopted the median estimated effect size: $\delta = .45$, which corresponds to what would commonly be described as a medium effect size. Following Raudenbush and Liu's (2000) recommendation,⁸ we set the residual error variance to 1 and estimated the between-subject slope variance to be 0.30. For power equal to .80 and $\alpha=0.05$, a sample size of 209 participants was indicated.

Based on the sample size calculations, using a sex-stratified random allocation table, we need a minimum sample of 209 participants to address Aims 1-3. To allow for 10% attrition from baseline to 48-week follow-up, we will recruit 230 participants.

Treatment Assignment Procedures

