9.3 Definition of Populations

Intention to Treat Analysis (ITT): We will include all randomized study participants who have at least baseline endpoint assessments in our ITT analysis. The ITT analysis is our primary method for assessing outcomes, and how it is performed will be determined based on the pattern of missingness. If the missingness is deemed MCAR, the LOCF method will be used: simply the most recent valid observation will be "carried forward" to replace the subsequent missing observations. If the missingness is deemed MAR, missing observations will remain as missing, and

maximum likelihood estimation, the default estimation algorithm of LMER, will be used to estimate these observations. If the missingness is found to be MNAR, multiple-imputed data will be used to construct LMER models.

Per-Protocol Analysis (PPA): For the PPA we will exclude study participants who: 1) fail to attend 13 out of 18 treatment sessions; 2) develop an exclusionary medical condition while on study protocol, or 3) receive interventions outside of the Allowed (Section 5.3.1) during treatment. Finally, we will assess how comparable estimated parameters vary between ITT and PPA analyses.

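### The protocol gives two different times for randomisation (Visit 0, or Visit 1 after baseline), and under the Visit 0 order the primary ITT set is not all randomised participants

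*Combined protocol and SAP*

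**What the plan says.** Three places point to Visit 0.

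- Section 4.3 describes consent, screening surveys, physical exam and enrolment, and then: "The study coordinator will then randomly assign them to their respective intervention group using a sex-stratified random allocation table". No baseline visit comes between.
- In the schedule (section 6.1), the row "Enrollment/Randomization" has its only mark under the Visit 0 screening column.
- Section 6.2.1 includes the "Enrollment & Randomization Form" among the items completed at Visit 0.

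One place points to Visit 1. Section 6.2.2 names Visit 1 in its heading and runs in the order enrolment, baseline assessments, randomisation. It states "Participants enrolled in the study will complete the following baseline assessments at Visit 1", and then gives a time limit: "A maximum of 7-days will be permitted between enrollment and randomization or initiation of the study intervention".

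Section 9.5.1 fixes the baseline of both co-primary outcomes at Visit 1. Section 6.1.1 allows up to 7 days from screening to that visit. Section 9.3 makes ITT the primary analysis and defines it so: "We will include all randomized study participants who have at least baseline endpoint assessments in our ITT analysis". Section 9.2 counts losses only from baseline onwards: "To allow for 10% attrition from baseline to 48-week follow-up, we will recruit 230 participants".

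**The concern.** A protocol needs one randomisation point, and staff working from section 4.3 and the schedule would allocate before baseline. Three things then follow.

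1. The set called ITT depends on an event after randomisation, namely completing the Visit 1 baseline. Exclusions made after allocation are no longer protected by randomisation.
2. Section 6.2.1 sends anyone who misses the 7-day deadline back through screening and consent under a new participant number. Such a person would already hold an allocation. The first record leaves ITT for lack of a baseline, and the second passes through section 4.3 again and could receive another allocation. No rule covers this.
3. A Tampa Scale score above 36 is an inclusion criterion (section 4.1), but the schedule first measures that scale at Visit 1. A person could be randomised and only then found ineligible, and section 10.3.4 lists randomising an ineligible subject as a protocol violation.

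**Working it through.** **Timing, side by side**

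| Place | When allocation happens | Relation to the Visit 1 baseline |
|---|---|---|
| 4.3 | Straight after screening exam and enrolment | Before |
| 6.1 schedule | Mark at Visit 0 only | Before |
| 6.2.1 | Form in the Visit 0 list | Before |
| 6.2.2 | Under Visit 1, listed after baseline assessments | After |

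The two orders cannot both hold. Section 6.2.2 does not settle the matter, because its 7-day limit runs to randomisation or, alternatively, to the start of intervention.

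**What each order does to ITT**

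- Order in 6.2.2: everyone randomised has attended baseline, so the condition in 9.3 should exclude few or none.
- Order in 4.3, 6.1 and 6.2.1: a person allocated at Visit 0 with no Visit 1 fails the condition. Pain and RMDQ are also taken at Visit 0, but 9.5.1 names Visit 1 as baseline and no passage lets the Visit 0 values stand in.

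**The plan's own numbers (9.2)**

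The recruited number reproduces: 209 × 1.10 = 229.9, so 230. (Dividing by the retained share gives 209 / 0.90 = 232.2, so 233.) After the planned loss, 230 × 0.90 = 207 remain at 48 weeks, 2 below 209. The 209 was calculated for Aims 2 and 3; section 9.2 then adopts it as the minimum for Aims 1 to 3.

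**Size of a loss before baseline**

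The documents give no rate q for people randomised but lost before Visit 1, so the q values below are assumptions. ITT = 230 × (1 − q); followed to 48 weeks = ITT × 0.90.

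| Assumed q | In ITT | At 48 weeks |
|---|---|---|
| 0% | 230 | 207 |
| 1% | 227.7 | 204.9 |
| 2% | 225.4 | 202.9 |
| 5% | 218.5 | 196.7 |
| 10% | 207 | 186.3 |

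The 10% allowance starts at baseline, so it covers none of this loss. If all visits fall on one day, which the note to the schedule permits, q could be close to zero.

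**The case against.** The case for reading the documents as baseline first is respectable. Two of the three Visit 0 supports concern a form. Section 6.2 says that form records the enrolment and randomisation dates, so it could be opened at Visit 0 and completed later, and 6.2.2 lists it as well. Section 4.3 gives an order of steps but names no visit for allocation. Section 6.2.2 dates enrolment to the point when all screening criteria are met; with the Tampa Scale first scheduled at Visit 1, that fits allocation at Visit 1. On this reading almost none of the harm arises. The argument shows that the Visit 0 order is not settled. It does not remove the conflict, since a coordinator following 4.3 and the schedule would act differently from one following 6.2.2.

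A reader might also infer more than the documents support:

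- *That baseline is in fact recorded after allocation.* Section 6.2.2 says the opposite, so this is one of two written orders.
- *That baseline scores are biased by knowledge of the arm.* Sections 5.2, 6.2.3 and 9.2 keep the data collection team blinded and bar the un-blinded coordinator from assessments. Both co-primaries are self-reports in a trial described as double-blind. Section 5.1 places the treatment rationale and first game exposure after all pre-treatment assessments. Pain and RMDQ are also recorded at Visit 0, as part of screening.
- *That loss before baseline differs by arm.* The coordinator both assigns the arm and schedules sessions, so a route exists, but nothing shows that it operates.
- *That the loss is 2% to 5%.* No figure in the documents supports any rate, and zero is within the plausible range.

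**Conclusion.** The point holds as an internal contradiction with a conditional consequence. Sections 4.3, 6.1 and 6.2.1 place allocation at Visit 0; section 6.2.2 places it at Visit 1 after baseline. If the first order is followed, the primary ITT set excludes randomised people who lack a Visit 1 baseline, repeat randomisation under a new number becomes possible, and allocation precedes the first scheduled measurement of an eligibility criterion. If the second is followed, the baseline condition in 9.3 does little, but the set is still not defined as all randomised.

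The number affected cannot be derived from the documents. Under the assumed 0% to 5%, between 0 and about 12 of 230 (230 × 0.05 = 11.5) would leave ITT, and 207 to about 197 would be followed to 48 weeks. Arm-dependent loss is possible but not shown; biased baseline scoring is not supported.

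**What to change.** - **Sections 4.3, 6.1 and 6.2.1:** state a single randomisation point at the end of Visit 1, in line with 6.2.2. It should come after eligibility is confirmed (including the Tampa Scale), after the baseline outcome assessments done at that visit, and before any arm-specific game parameters are loaded. The activity monitor is worn for the week after Visit 1, so its data necessarily come later.
- **Section 9.3:** define ITT as all randomised participants. The model in 9.6 treats the pre-treatment value as one level of time, so a missing baseline need not remove a record.
- **Section 6.2.1:** add a sentence confining re-screening under a new number to people not yet randomised. The 7-day deadline there covers Visit 2 as well as Visit 1, so moving randomisation does not by itself close this gap.

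The cost is wording in four sections. No visit, staff member or participant is added, and Visits 0, 1 and 2 may still fall on one day.
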